As a result of the COVID-19 pandemic, some activities will be move to being offered by phone. For adolescents, study activities conducted by phone pose potential additional risks of inadvertent disclosure of adolescent HIV status for participating adolescents. However, healthcare providers already routinely call adolescents to remind them of clinic visits and support groups, and may be moving to provide more services by phone to minimize exposure at clinics during the COVID-19 pandemic. To minimize potential disclosure risks, we will first confirm that the person on the phone is the enrolled study participant. We will also ask the participant to confirm willingness to participate in phone-based activities. We are also only offering services to adolescents who know their status, as part of the inclusion criteria for enrolling in the transition intervention activities.

12a. Informed Consent Process

Clinic participation

This intervention will be at facility level therefore, we will engage with the relevant HIV care partners, county health management and facility administration teams prior to entering health facilities. Because we will be collecting routinely collected program data on adolescent retention and health outcomes, we will request a waiver of individual consent of adolescent patients for abstracting clinic records.

HCW and Policy makers and administrators

HCW participants will provide written informed consent for participation in IDIs, FGDs, implementation evaluation activities, and the working group.

For post-trial surveys among HCWs, we will request waiver of written consent as no identifying information will be collected.

Policy makers and administrators will provide written informed consent for participation in IDIs.

Adolescent patients

The consent and assent process for IDIs and FGDs by age is described below:

- 1) Adolescents ages 14-17 who come with a caregiver: Written informed consent will be sought from the caregiver and written assent will be sought from the minor. We will not enroll any adolescent between ages 14 and 17 who is unaccompanied by a caregiver.
- 2) Adolescents >18: Regardless of whether they are accompanied, adolescents will provide written informed consent.

Pre and post- trial surveys: We will request a waiver of written assent or consent for these participants. We will also request a waiver of parental permission for adolescents ages 12-17. As we will not be collecting any personal information, breach of confidentiality is of higher risk with written documentation rather than verbal agreement. We request waiver of parental consent because many adolescents attend the care clinic independently, without their caregivers. If caregivers are present with the child participant, we will respect caregivers' wishes if they do not want the child to complete the anonymous survey. Requirement of parental consent would be problematic for adolescents who have transitioned (eg, have assumed autonomy for their own care), and for those whose caregivers would be unavailable to come in and provide consent. Excluding these adolescents would bias the study population.

Transition readiness surveys: Written informed consent or assent will be sought from the adolescent ages 10-24 years. We will request a waiver of parental permission for adolescents ages 15-17 years because many adolescents present to clinic for care unaccompanied and the survey questions are minimal risk and ask about non-sensitive information. Requirement of parental consent would be problematic for adolescents 15-17 years who have attained full disclosure and potentially transitioned (e.g., have assumed autonomy for their own care), and for those whose caregivers would be unavailable to come in and provide consent. Excluding these adolescents would bias the study population.

Caregivers of HIV-infected adolescents

Caregivers will provide written informed consent.

Consent Details:

A consent form describing in detail the study procedures and risks will be provided. Participants will be informed that they are free to decline participation, and that declining to give permission will have no impact on their role in this study. Participants will be informed that they are free to withdraw their permission at any time during the study.

Consent forms and information sheets will be IRB-approved, and the participant is required to read and review the document or have the document read to him or her. The study team member will explain the research study to the participant and answer any questions that may arise. The individual will sign the informed consent document prior to any study-related assessments or procedures. Participants will be given the opportunity to discuss the study with their surrogates or think about it prior to agreeing to participate. They may withdraw consent at any time throughout the course of the study. A copy of the informed consent document will be given to participants for their records. The rights and welfare of the participants will be protected by emphasizing to them that the quality of their clinical care will not be adversely affected if they decline to participate in this study.

Comprehension will be assessed by asking the participant to repeat back what was explained and encourage them to ask questions. Study staff may ask the participant questions like the following to assess comprehension:

- b) "Just so that I'm sure you understand what is expected of you, would you please explain to me what you think we're asking you to do?"
- c) "Describe in your own words the purpose of the study."
- d) "What more would you like to know?"
- e) "What is the possible benefit to you of participating in this study? What are the possible risks?"

If the participant is unable to answer these questions, study staff will go through the consent form with them again. If a participant continues to be unable to understand the study procedures and risks and benefits, the staff person will thank them for their time and let them go without enrolling them into the study.

For all participants that are unable to read, we will ensure that the consent form is read aloud to them and that there is a witness present when they sign the consent form. We will ensure that the witness also signs the form documenting observation of the consent process and the participant's willingness to participate.

Exclusion of Women, Minorities, and Children

There are no exclusions of women or minorities. Eligibility is based on age and occupation. Adolescent patients under age 6 will be excluded from this study because the target population is children, adolescents and youth ages 6-24.

Translation of Materials:

We anticipate that the majority of study participants will be fluent in either Kiswahili, Luo, or English or other language appropriate for where the research study is taking place. We will generate study materials specific to each of those languages. For interviews and focus group discussions, we will ensure that the interviewer is fluent in the preferred language spoken by patients at the clinic.

We will not provide interpretation services. We will require that our research coordinator(s) and qualitative study staff be fluent in English, Swahili, Luo or another local language spoken in the region where research is taking place. Only participants who understand English, Swahili and/or Luo or another language appropriate for where the study is taking place will be eligible for the study.

At least 1 study staff member will be fluent in every language we will be creating consent and other study related materials for. We will ensure that participants speak with a study staff member fluent in their preferred language when they have questions or concerns about the study.

We will work with translators/interpreters who are fluent in English, Swahili, and other relevant tribal languages to translate consent forms to the appropriate languages. Once consents are translated and transcribed into their appropriate language, they will be back translated to English by another translator/interpreter who has not seen the original English consent form to ensure that the messages and material included in the consent form is accurate. We will correct any information in the translated consents that is not correctly back translated and get approval from the ERC for all translated study materials.

12b. Participant Confidentiality

All key personnel will be trained in the Protection of Human Subjects. The field team will take every precaution to protect participants' confidentiality. To ensure confidentiality, focus group discussions and interviews will take place in rooms where the door to the room can be shut during the discussion. Only designated study staff and the individuals involved in the focus

group discussion or interview will be allowed in the room during the focus group discussion or interview.

We only will collect personal identifiers for the purposes of identifying and contacting participants about the study. This information will include the names, telephone numbers and emails for those identified as interested in participating in the study. We will not collect patient identifiers for participants completing pre, during and post-trial anonymous surveys. Personal identifiers will be used to contact participants to remind them of their upcoming study visit and also to contact them if they fail to appear for their scheduled study visit. This information will also be used to contact them again to verify the accuracy of the information collected or to elaborate or clarify certain information provided during study procedures if they select the option to be re-contacted on the consent form.

All participants will be assigned a study identification number (ID). Health information and phone numbers will be recorded and stored under this study ID. Participant identifiers will be linked to their study ID and will be stored in binder in a locked cabinet separately from all other study data. Only necessary study staff will have linkage to this linkage binder.

A limited number of study staff will have access to patient identifiers and will not share this information with other study staff or with others outside of this study. Links between patient identifiers and unique study IDs will be kept for a maximum period of 6 years after the study has ended, at which time the link between patient IDs and identifiers will be destroyed. All consent forms will be kept in locked offices and file cabinets, and will be in separate files from data with identifiers.

Study staff will take strict measures to maintain confidentiality for participants. Data collected will be kept confidential and access restricted to study staff. All audio-recordings of the IDIs will be kept in a secure database. All other data will be kept in password-protected databases, in a locked study office, accessible only to study personnel. Study identifiers will be linked to coded data; clinical staff will have access to patient identifiers, but the analysts will receive only coded data. Links between patient identifiers and study codes will be kept for a period of 6 years after the end of the study, at which time the link between patient IDs and codes will be destroyed.

12c. Potential Risks and Benefits

Potential Risks

- *Physical:* There are no medical interventions associated with the study, therefore we anticipate no risk of serious harm to participating HCWs, adolescents, caregivers, hospital administrators or policy makers.
- *Other:* Other study risks include emotional distress associated with the sensitive nature of the disclosure process, breach of patient confidentiality during data extraction (adolescent clinic records), and fear of or actual loss of employment associated with implementing the ATP. We are not directly enrolling adolescent clients other than to take part in in-depth interviews, focus group discussions, and anonymous surveys. However, there is a possibility for social harm (depression, violence after disclosure, abandonment) related to disclosure of HIV status during clinical encounters at HIV care. However, the possibility of this social harm would exist if this intervention were not conducted. For the FGDs, it is also possible that a participant may know another member in the discussion and by participating in the discussion the other member might learn of their HIV status. We have outlined this potential risk in the consent form.

- *Other:* There is a possibility that during a clinical encounter with a HCW using the more comprehensive tools that are part of the adolescent transition package that an adolescent patient may be more comfortable disclosing that they are suffering from previously undiagnosed mental health problems such as depression. Any patients with potential mental health problems will be referred for psychosocial support at the facility or nearest referral hospital, according to standard HIV care and treatment guidelines for adolescents at that clinic and within the country.
- *Alternative treatments or procedures:* Not applicable
- *Procedures to minimize psychological risks:* All participants will be assured that their participation is voluntary and that they may withdraw from the study at any time. Study personnel experienced with adolescents will perform the disclosure intervention. Adolescent participants will be informed that they can skip any question or stop the interview, focus group or surveys at any time. We will ask all the members in focus group discussions to protect each other's privacy, and not to repeat anything that is said or learned once the discussion is over.
- *Procedures to minimize other risks:* Study staff will be trained to take all precautions to ensure confidentiality of participation and data collected, and will have standardized operating procedures to follow to minimize the risks of a participant's loss of confidentiality. Risk of breach of confidentiality of study data is low, as all patient data collected will not include names and will be located on a password protected server, and encrypted prior to upload. Study staff will be trained in the importance of confidentiality during human participants training prior to study implementation.
- The systematic disclosure approach will minimize the possibility of involuntary disclosure of HIV status to an adolescent. Some adolescent patients are receiving HIV care and take ART (which may be called 'medicine' and not HIV medicine), but may not yet know their HIV status, because the caregiver is not ready for the child to learn this information.
- *Additional protection for children:* Additional protections will be afforded to participants in the in-depth interviews or focus group discussions. These protections will depend on adolescents' age and whether they are accompanied by a caregiver. Adolescents accompanied by caregivers will be given the option of having their caregiver present during the interview or focus group. Adolescents will also be given the opportunity to meet with a nurse counselor, or other similar staff member, if they request to see one or if the interviewer believes they should see one following the interview or focus group discussion.

Potential Benefits

- *HCWs and clinics:* HCWs in the intervention sites will receive direct and immediate benefit in receipt of disclosure skills and transition tools that may improve outcomes in their facilities.
- *Adolescent client (clinic attendees):* Adolescent clients of participating health facilities may benefit directly from the improved disclosure services and transition services they receive from trained HCWs.

Unanticipated Problems

In compliance with federal regulations and UW policy, the Principal Investigator will notify the UW Human Subjects Division (HSD) and or UW Institutional Review Board (IRB) of any unanticipated problems within 10 business days and the Kenyan Ethics Committee, and relevant local Kenyan authorities (i.e. Ministry of Health) within 3 business days. Any breach or possible breach of confidentiality of any participants in this study will be reported to UW HSD and/or IRB within 24 hours.

Data Safety and Monitoring

A DSMP is not required for this study. However, we are planning to create an External Advisory Panel (EAP) to act in an advisory capacity to the National Institute of Child Health and Human Development (NICHD), the University of Washington, School of Medicine, and the University of Nairobi, to monitor recruitment, enrollment, and potential social harms of the intervention.

SECTION 13: USE OF INFORMATION AND PUBLICATIONS

Study results will be presented to all participating sites at the end of the study period. This study will comply with the [NIH Public Access Policy](#), which ensures that the public has access to the published results of NIH funded research. It requires scientists to submit final peer-reviewed journal manuscripts that arise from NIH funds to the digital archive [PubMed Central](#) upon acceptance for publication.

SECTION 14: LIMITATIONS

We recognize that clinics utilizing EMR systems for capturing patient information may not be representative of all clinics in Kenya and that selecting only sites with EMR systems in place may limit the generalizability of our findings in Aim 1 regarding current systems in place for adolescent HIV treatment and care.

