As many HIV-infected children on ART survive to adulthood in sub-Saharan Africa, improving systems for disclosure and transition to adult care is a high priority. There is need for better data on transition in high volume HIV clinics in Africa, and these clinics require feasible, effective systematic approaches to improve disclosure and transition. A disclosure tool used in Namibia demonstrates effectiveness and acceptability and could be adapted for use in other settings. In addition, the Got Transition model, which was developed following broad expert consensus and programmatic evaluation in US settings, has a clear framework and useful resources relevant to pediatric HIV transition in Africa. Combining these interventions using an implementation science

approach (program evaluation, adaptation and a cluster RCT) has potential to provide high quality evidence for broader use of these approaches and to improve long-term outcomes for adolescents with HIV.

SECTION 2: OBJECTIVES

2a. Study Objective

This study aims to evaluate rates and co-factors of effective transition in HIV treatment programs in Kenya and to adapt, implement, and evaluate an Adolescent Transition Package (ATP) that combines an adapted US-based transition tool and a disclosure tool associated with improved disclosure outcomes in Namibia.

2b. Specific Objectives

Aim 1: To use programmatic data (KenyaEMR and paper files) to estimate prevalence of transition and disclosure, age at transition and disclosure, and individual-level co-factors of effective transition from pediatric to adult HIV care and retention and HIV disclosure among 10-24 year olds. To determine transition practices in Kenyan clinics using a facility survey.

Effective transition will be defined as enrollment into adult care within 6 months of exiting the pediatric care and continued clinical follow-up for at least 6 months thereafter, as evidenced by a second clinic visit recorded in the EMR.

Hypothesis: Transition will occur at varied ages (median 18 years); effective transition and earlier transition age will be associated with the presence of a transition plan and adolescent friendly services at the facility, later age at child HIV diagnosis, earlier age of HIV disclosure, parent on ART, better health status of the child at enrollment into HIV care and at transfer (CD4, WHO stage, viral load), pregnancy or marital status of the adolescent, and evidence of consistent adherence and retention prior to transition.

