Approach: *We will randomize 20 clinics to receive the ATP or no intervention (SOC) and compare disclosure and appropriate transition using pre-specified milestones among a group of children and adolescents with heterogeneous ages. During early implementation, we will monitor fidelity to the intervention using modified plan-do-study-act (PDSA) cycles. We will track implementation outcomes and factors influencing implementation during the initial ATP implementation phase (6 months). During this time, the study team will discuss and support changes to refine the tool as needed at each facility. Following the initial implementation period, HCWs will take part in focus group discussions to share their suggestions for optimizing the transition tool based on their experience. Understanding personal experiences with the tool will provide an opportunity for lessons learned and continued refinement of the intervention. At the end of the study, we will qualitatively evaluate acceptability, appropriateness and feasibility of the ATP by conducting interviews and FGDs with all HCWs from implementing sites and adolescents from a sub-set of intervention sites, purposively selecting to include participants from high and low performing facilities. We will also conduct pre-trial and post-trial surveys with adolescents and HCWs to quantitatively assess acceptability, appropriateness, feasibility of the ATP and implementation intervention fidelity. At 6-monthly intervals, we will collect readiness assessment information from adolescents in participating clinics.*

SECTION 3: STUDY OUTCOMES

Aim 1

- Prevalence of transition
- Age at transition
- Co-factors for retention
- Age at disclosure
- Co-factors of disclosure
- Individual level co-factors of effective transition
- Facility level co-factors of effective transition

Aim 2

- Adapted transition tool

Aim 3

- The primary outcome is **disclosure** among non-disclosed adolescents and **effective transition and transition readiness** among disclosed adolescents

- Disclosure will be defined as no, partial or complete disclosure. Time to disclosure and age at disclosure will also be assessed.
- Effective transition with retention in care will be defined as completing a visit on the adult day or completing a visit without a caregiver and repeat visits continuing for at least 6 months after transition.
- Transition readiness will be defined as change in response to readiness assessment questions administered every 6 months

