For each clinic that agrees to participate, routine clinic data will be abstracted from the EMR system and from paper forms when EMR systems are not available. The medical records collected from the patient charts will include data tracking routine services offered and laboratory measurements collected. EMR or other medical record data will be abstracted directly from clinics or from implementing partners, whichever is most convenient for the clinic. If data staff at the partner organization or at the clinic are unable to extract the data on their own, hired technicians or study staff will travel to sites and assist with data abstraction directly. All medical records for adolescents ages 10-24 attending the clinic at least 1 time between January 1, 2016 and the date of data abstraction (but not later than December 31, 2017) will be pulled.

Data Collection Procedures:

For EMR data, data will be extracted by running a standardized query of the EMR database. The query will pull serial records for all adolescents ages 10-24 years who have at least 1 visit on or following January 1, 2016 and attend a clinic selected to participate in the facility survey. This will include all data on each adolescent from January 1, 2016 up until the date when data is abstracted but not later than December 31, 2017. We will not obtain individual consent for pulling adolescent records from the EMR. We will obtain a waiver of consent to obtain this information. Data collected will obtain basic demographic and HIV-specific clinical care outcomes as detailed in the attached file listing variables to be collected. This information is already charted as part of routine care. For paper records, data will be abstracted using Case

Report Forms (CRFs) and Open Data Kit (ODK) or REDCap. We will abstract selected variables from the EMR and paper based records including: client age at enrollment, caregiver type, sex, date/age of HIV diagnosis, CD4 count or percent, date of ART initiation, attendance at pediatric or adult clinic day (data obtained from facility survey and calculated by visit dates), and presence of caregiver at the visit (in EMR counseling notes). Serial data will be obtained on follow-up at the clinic. A list of variables that will be collected is attached.

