- *Prospective Data - Demographic information:* We will collect demographic information for all participating in the FGD/IDIs. Demographic surveys for each population included in IDIs or FGDs are attached as appendices.
- *Retrospective and Prospective Data - Clinic records:* Adolescent clinic records from the EMR system and routinely collected paper forms will be extracted from all clinics participating in Aim 1 and at baseline, and throughout the RCT, for clinics participating in Aim 3 to assess clinical adolescent outcomes. Data from each pull will capture all records until the previous data pull (Aim 3) or from between January 1, 2016 and December 31, 2017 (Aim 1). Examples of data will be enrollment age, CD4, viral load (where available), WHO stage, hospitalization, caregiver presence, serial visits since enrollment, pediatric or adult clinic day of attendance and reported adherence. This will be collected from the clinic medical records database or paper clinic records, a clinic partner organization, or other location where medical record data for selected clinics is being stored and managed such as the Kenyan National Data Warehouse.
- *Prospective Data - Disclosure checklist:* This will be completed at every clinic visit to obtain more detailed data on partial and full disclosure in both intervention and control sites. This data will be abstracted from patient files routinely throughout the RCT.
- *Prospective Data - Transition booklet tracking form:* This will be completed at every clinic visit to obtain more detailed data on transition in intervention sites. This data will be abstracted from patient files routinely throughout the RCT.
- *Prospective Data - Transition tracking log:* This will be completed at transition to adult clinics and for next 6 months for both intervention and control sites. This data will be abstracted from patient files routinely throughout the RCT. .
- *Prospective Data - Pre-Trial surveys:* Surveys will be conducted with adolescents who have completed disclosure or transitioned to adult care and HCWs from intervention sites. Adolescent surveys will be conducted for both intervention and control sites at the beginning of the study. Information will include basic demographics (age, schooling) and satisfaction with services received. HCW surveys include basic demographic information, initial impressions of the ATP, and implementation climate.

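### Aim 1: the stated data window (1 January 2016 to 31 December 2017) conflicts with cofactors and retention analyses that need earlier records; the plan should say whether the start date limits eligibility or the data

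*Combined protocol and SAP*

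**What the plan says.** The Aim 1 hypothesis in Section 2b links effective and earlier transition to several cofactors. Three depend on history: "better health status of the child at enrollment into HIV care and at transfer (CD4, WHO stage, viral load", "earlier age of HIV disclosure, parent on ART" (the disclosure part) and "evidence of consistent adherence and retention prior to transition". Section 3 also lists "Age at disclosure" as an Aim 1 outcome.

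Two places put dates on the data themselves:

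- Section 7a (programmatic data, data collection procedures), describing the EMR query: "This will include all data on each adolescent from January 1, 2016 up until the date when data is abstracted", closed by "but not later than December 31, 2017".
- Section 10 (clinic records), covering EMR and paper records alike: "from between January 1, 2016 and December 31, 2017 (Aim 1".

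Other text points the other way:

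- Table 4 and Section 11a use 1 January 2016 only as a visit-eligibility date. The opening of Section 7a likewise pulls the records of anyone with a qualifying visit.
- Section 10, in the same item as its date range, lists "serial visits since enrollment" as an example of data to be obtained.
- Section 7a names stored historical fields: age at enrollment, date or age of diagnosis, and ART start date.
- Section 11b plans retention at 6, 12 and 36 months, with the denominator based on enrollment date.

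**The concern.** A standardised query run on the Section 7a wording returns no result dated before 2016. For a youth who entered HIV care earlier, the CD4, WHO stage and viral load measured at entry would not be returned. The analyst could then restrict the enrollment-status analysis to youth who entered care in 2016 or later, or let the first value seen in the window stand in for the enrollment value. The first changes the population and the second changes the exposure.

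Prior retention has a different problem. Its observable history runs from 1 January 2016 to the transition date, so a score built on it partly reflects when in the calendar the youth transitioned.

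**Working it through.** **1. The plan's own Aim 1 figure.** Inputs from Section 11a: p = 0.60, half-width d = 0.025, 95% confidence, ICC = 0.05, 50 adolescents per clinic.

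- n = 1.96² × 0.60 × 0.40 / 0.025² = 1,475.1
- Design effect = 1 + (50 − 1) × 0.05 = 3.45
- 1,475.1 × 3.45 = 5,089.2; divided by 50 = 101.8, so 102 clinics

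This reproduces. It depends on the number of adolescents, not on how far back each record goes, so the window does not disturb it.

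**2. Length of the window.** 1 January 2016 to 31 December 2017 is 731 days; 731 / 30.4375 = 24.0 months at most.

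**3. Retention at 36 months.** A youth enrolled on the first day of the window is followed for at most 24 months, 12 short of 36. With a stored enrollment date, the 36-month mark falls inside the window for youth enrolled from January 2013 to December 2014. They enter the data only if they attended in 2016 or later, so losses before 2016 are unseen.

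**4. Look-back before transition.** Section 2b defines effective transition as adult enrollment within 6 months of pediatric exit, then at least 6 months of follow-up.

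| Time from exit to adult enrollment | Latest exit that can be fully scored | Look-back in window |
|---|---|---|
| Full 6 months | 24 − 12 = month 12 (end December 2016) | 0 to 12 months |
| Immediate | 24 − 6 = month 18 (end June 2017) | 0 to 18 months |

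If transitions were spread evenly (an assumption), the mean look-back would be 6 or 9 months.

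**5. The two readings side by side.**

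| Item | Date is eligibility only | Date also limits the data |
|---|---|---|
| Dated CD4, WHO stage, viral load at enrollment | Captured where recorded | Not captured if enrolled before 2016 |
| Adherence and retention before transition | Full recorded history | Left-truncated at 1 January 2016 |
| Age at disclosure | Captured where recorded | Disclosures in the window; earlier ones only if a date or age is stored |
| 36-month retention from enrollment | Follow-up recorded, given attendance in 2016 or later | Cannot be followed from enrollment |
| Age at enrollment, diagnosis, ART start | Stored field | Stored field |

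**6. Possible size for enrollment values.** The share enrolled before 2016 is not given, so it is varied here as an assumption. The base is 102 × 50 = 5,100 adolescents.

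| Assumed share enrolled before 2016 | Most who could have enrollment values in the window |
|---|---|
| 25% | 3,825 |
| 50% | 2,550 |
| 75% | 1,275 |
| 90% | 510 |

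These are ceilings for all adolescents. The number who also transitioned, with follow-up complete, would be smaller.

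**The case against.** The best defence is that 1 January 2016 was meant only as an eligibility date. Table 4, Section 11a and the opening of Section 7a say so, and the visit history in Section 10 and the 36-month retention in Section 11b make sense only on that reading. This stands as evidence of possible intent. It does not remove the problem, because the two sections that describe what is extracted set the lower limit on the data.

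A second defence is that the full variable list is an attachment not shown here. It may hold a disclosure date or a stored baseline CD4 or WHO stage. That stands too: stored fields would reduce the loss, and Section 7a already takes several. Section 11b does not list enrollment clinical values or age at disclosure among its transition cofactors, but its list is not exhaustive and the Section 2b hypothesis remains.

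A third is practical. Aim 1 data end in 2017, while this version of the protocol includes COVID-19 procedures and an analysis plan finalised in February 2020. Section 7a says original files with patient identifiers are not kept, and Section 10 collects viral load only where available. These points limit what can be recovered after extraction, but not the need to state which reading was used.

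A reader might infer that all three history-dependent cofactors are missing for nearly everyone enrolled before 2016, or that the Aim 1 hypotheses go untested. The documents support neither. Prior retention is truncated, not missing. Disclosures in the window are observable whenever the youth enrolled. The window does not by itself remove a facility transition plan, adolescent-friendly services, age at diagnosis, parental ART, health status at transfer, or pregnancy and marital status.

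**Conclusion.** The contradiction is real and worth resolving. Sections 7a and 10 limit the Aim 1 data to 24 months; Table 4 and Section 11a do not, and Section 11b plans an analysis that cannot fit. If the limit is applied as written, enrollment-time clinical values are lost for youth enrolled before 2016 unless stored as baseline fields. Prior retention is left-truncated by an amount that varies with calendar date, and 36-month retention cannot be followed from enrollment.

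The calendar results rest only on the plan's dates and its definition of effective transition. The size of the loss is unknown: the table in step 6 is an assumed range, and any single percentage would need a time-in-care distribution that the documents do not give. The point concerns observational Aim 1 cofactor and retention analyses. It does not touch the Aim 1 precision calculation or the cluster trial's primary analysis of transition readiness.

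**What to change.** Reconcile Sections 7a and 10 with Sections 2b, 11a and 11b. Keep 1 January 2016 as the eligibility date and lift the lower date limit for cofactor fields, so that the query returns, whatever the date:

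- the first recorded CD4, WHO stage and, where available, viral load after enrollment;
- the recorded date or age of full disclosure;
- all visits in a fixed look-back before transition, for example 12 months, used to score prior retention for everyone.

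Lifting the limit does not bring back youth lost before 2016. Retention from enrollment should therefore be described as conditional on attendance in 2016 or later, with delayed entry in the Cox model.

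At the planning stage the cost is one change to the query, some extra paper abstraction, and possibly an update to the date range in the consent waiver.

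If extraction is complete, a new pull could involve up to 102 sites. The sponsor should then state which reading was used and restrict the enrollment-status and prior-retention analyses to youth with the needed data in the window. The 36-month figure should be limited to youth whose 36-month mark falls in the window and labelled as conditional, or dropped.
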